3.3 Exploratory Endpoints

3.3.1 [REDACTED]

3.3.2 [REDACTED]

3.3.3 [REDACTED]

4.0 SUBJECT ELIGIBILITY

In order to participate in this study a subject must meet ALL of the eligibility criteria outlined below. All study screening evaluations must be completed within 21 days of subject enrollment.

4.1 Inclusion Criteria

- 4.1.1** Newly diagnosed or previously treated subjects with KSHV-associated MCD that is pathologically confirmed by characteristic histologic features and latency-associated nuclear antigen (LANA) positivity by IHC.
- 4.1.2** Age ≥ 18 at time of consent.
- 4.1.3** Can provide informed consent.
- 4.1.4** HIV-infected or HIV-uninfected.
- 4.1.5** If HIV-infected, must be on or willing to start antiretroviral therapy including lamivudine or tenofovir.
- 4.1.6** Willing to comply with study visits.
- 4.1.7** MCD treatment indicated based on the presence of a symptomatic MCD flare, defined as the presence of each of the following three criteria:
 - 1. Fever (subjective or objective)
 - 2. Lymphadenopathy or hepatosplenomegaly
 - 3. At least one of the following signs or symptoms attributable to MCD by the local study investigator:
 - Weight loss $>5\%$
 - Malaise
 - Anemia (Hemoglobin <10 g/dL) within the past 4 weeks
 - Thrombocytopenia (Platelets $<100 \times 10^3/\mu\text{L}$)
 - Note that if only two of the three criteria are present, but the provider feels treatment is indicated for a symptomatic MCD flare, this will be allowed after communication with the study principle investigator (PI).
 - Note that subjects with low hemoglobin within the past 4 weeks that have since received a blood transfusion are still eligible for participation. The subject's

pre-transfusion hemoglobin value will be considered when determining risk classification.

4.1.8 Females of childbearing potential must have a negative urine pregnancy test within three days prior to registration.

- Note that females are considered of childbearing potential unless they are surgically sterile (have undergone a hysterectomy, bilateral tubal ligation, or bilateral oophorectomy) or they are naturally postmenopausal for at least 12 consecutive months. Documentation of postmenopausal status must be provided.

4.1.9 Females must agree to abstain from breast-feeding during therapy and for 6 months after the completion of therapy.

4.1.10 Females of childbearing potential must be willing to abstain from heterosexual activity or to use two forms of effective methods of contraception from the time of informed consent until 12 months after treatment discontinuation. The two contraception methods can be comprised of two barrier methods, or a barrier method plus a hormonal method, or an intrauterine device that meets <1% failure rate for protection from pregnancy in the product label.

4.1.11 Male subjects with female partners must have had a prior vasectomy or agree to use an adequate method of contraception (i.e., double barrier method: condom plus spermicidal agent) starting with the first dose of study therapy through 6 months after the last dose of study therapy.

4.1.12 At least 7 days without corticosteroid use prior to start of treatment.

4.2 Exclusion Criteria

All subjects meeting any of the following exclusion criteria at time of enrollment will be excluded from study participation.

4.2.1 Symptomatic, extensive-stage KS (T1 by the ACTG staging system; T1 includes ulceration or edema from KS, raised or non-hard palate oral lesions, or any visceral

involvement) requiring urgent treatment, to avoid potential rituximab-induced KS worsening.

- 4.2.2** Previous rituximab use for MCD.
- 4.2.3** Second active malignancy requiring systemic therapy.
- 4.2.4** If HIV negative and a) hepatitis B virus surface antigen positive or unless on tenofovir or lamivudine. All HIV-infected patients must be on tenofovir or lamivudine as part of the inclusion criteria.
- 4.2.5** Active infection requiring systemic therapy.
- 4.2.6** Treatment with any investigational drug within 28 days prior to registration.
- 4.2.7** More than 7 days of corticosteroids immediately prior to enrollment. If subject is taking corticosteroids for more than 7 days, they require a 7 day washout period before enrollment.
- 4.2.8** Bilirubin >3 mg/dL.
- 4.2.9** Creatinine clearance <30 ml/min by Cockcroft-Gault formula.
- 4.2.10** ECOG performance status >3.
- 4.2.11** Pregnant or breastfeeding (NOTE: breast milk cannot be stored for future use while the mother is being treated on study).

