5.4.4 Antiretroviral therapy

Antiretroviral therapy (ART) is not prescribed by the study protocol and, according to Malawi national guidelines, is left to the discretion of treating HIV clinicians. Study clinicians will collaborate with HIV clinicians to ensure receipt of ART concurrently with chemotherapy. Zidovudine-based treatment will be strongly discouraged to avoid additional myelosuppression.

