7.2.4 Hepatitis B serologies

Hepatitis B surface antigen will be assessed for all HIV negative subjects at baseline.

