8.0 EVALUATIONS AND ASSESSMENTS

8.1 Time and Events Table (Table 7)

Table 7: Time and Events Table.	Initial Visit or Relapse ¹	Treatment days 1, 8, 15, and 22 ²	End-of-treatment (Week 5)	Follow-up (12 weeks)	Long term follow up ⁴
Informed consent	Initial visit only				
History & physical exam ⁵	X	X	X	X	X
Concomitant medications ⁶	X	X	X		
ECOG performance status ⁷	X	X	X		
Toxicity evaluation ⁸	X	X	X	X	X ⁸
Tumor biopsy ⁹	X				
Survival ¹⁰		X	X	X	X
Treatments ¹¹		X			
Lymph node measurements	X	Day 15 only	X	X	X
MCD-SS and Quality of life assessment ¹²	X	Day 15 only	X	X	X ¹²
Chest X-ray and abdominal ultrasound	X		X ¹³		
Hematology & blood chemistries ¹⁴	X ¹⁵	X ¹⁶	X	CBC only	CBC only
Correlative blood samples ¹⁷	X	Day 15 only	X	X	X ¹⁹
Lactate dehydrogenase	X	Day 15 only	X		

Viral and host genotyping	X	
Urine pregnancy test	X ¹⁸	
Hepatitis B (for HIV-negative patients)	X	
CD4 and HIV RNA (if HIV positive)	X	X ¹⁹

¹ Screening assessments must be completed within 21 days prior to study enrollment.

² A window of +/- 7 days will apply to all study visits; however, lymph node measurements must take place prior to that cycle's treatment.

³ End-of-treatment visit should occur 7-14 days from final dose of chemotherapy. A subject who is being withdrawn for disease progression or for other reasons (e.g. unacceptable toxicity, etc.) should complete an end of treatment visit.

⁴ Long term follow-up will occur every 3 months until 24 months after the start of treatment unless otherwise noted.

⁵ After the initial visit (comprehensive history and physical exam) subsequent visits will address a focused history and physical exam.

⁶ All concomitant medications will be recorded.

⁷ See Appendix E. ECOG Performance Status

⁸ per NCI CTCAEv5.0 for notation of baseline toxicity. Assess from initial visit through first follow-up visit (12 weeks) and again at the final follow up visit (24 months).

⁹ Archival and/or fresh sample.

¹⁰ Survival will be assessed at each visit through out the duration of treatment, follow up, and long term follow up.

¹¹ Subjects with low risk disease will receive rituximab at 375 mg/m² weekly for 4 weeks. High risk subjects will receive rituximab at 375 mg/m² and etoposide at 100 mg/m² weekly for 4 weeks.

¹² Quality of life assessment includes PROMIS Global 10, MCD-SS and QoL will be assessed through follow up, and at 24 months during long term follow up. QoL will also be assessed at the time of any relapse.

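### HIV-infected patients are exempt from hepatitis B testing because 4.2.4 takes them to be on tenofovir or lamivudine, but inclusion 4.1.5 does not require either drug before the first rituximab dose

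*Combined protocol and SAP*

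**What the plan says.** Section 4.2 opens with: "All subjects meeting any of the following exclusion criteria at time of enrollment will be excluded from study participation". Item 4.2.4 then excludes an HIV-negative patient who is HBsAg positive and not taking tenofovir or lamivudine. It sets no antigen rule for HIV-infected patients and gives the reason: "All HIV-infected patients must be on tenofovir or lamivudine as part of the inclusion criteria".

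The inclusion criterion it relies on is 4.1.5: "If HIV-infected, must be on or willing to start antiretroviral therapy including lamivudine or tenofovir".

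Testing follows the exclusion. Section 7.2.4 states: "Hepatitis B surface antigen will be assessed for all HIV negative subjects at baseline". The matching row in Table 7 (section 8.1) begins "Hepatitis B (for HIV-negative patients". Neither schedules the test for an HIV-infected patient.

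On ART itself, section 5.4.4 says "Antiretroviral therapy (ART) is not prescribed by the study protocol" and leaves it to the treating HIV clinicians, then adds: "Study clinicians will collaborate with HIV clinicians to ensure receipt of ART concurrently with chemotherapy". Section 6.1.6 reports liver failure and death from hepatitis B reactivation under rituximab. It advises screening people at high risk beforehand and monitoring known carriers.

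**The concern.** The protocol protects HIV-negative patients from reactivation by testing, and HIV-infected patients by antiviral cover. The second protection is stated as a fact drawn from the inclusion criteria, yet the criterion cited does not deliver it, because willingness to begin a drug is not cover. A patient who has agreed to ART but not begun it may have neither protection on the day of the first infusion.

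What is at stake is patient safety in a small subgroup, together with an eligibility rule that two sites, or two investigators at one site, could apply differently. No statistical quantity depends on it.

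**Working it through.** No arithmetic is needed to establish the point. The check is to take one HIV-infected patient who is not on ART and agrees to start, and follow that patient through the current text.

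| Step | If 4.1.5 governs | If 4.2.4 is a requirement in its own right |
|---|---|---|
| Inclusion 4.1.5 | Met by agreement to start | Met by agreement to start |
| HBsAg exclusion in 4.2.4 | Not applicable (HIV-negative only) | Not applicable (HIV-negative only) |
| Tenofovir or lamivudine at enrollment | Not required | Required |
| HBsAg test (7.2.4, Table 7) | Not scheduled | Not scheduled |
| ART before the first dose (5.4.4) | Encouraged, no date | Already begun, by eligibility |
| Result on day 1 | May be dosed untested and uncovered | Ineligible unless ART begins before enrollment |

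Three further checks:

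1. *Is either criterion superseded?* No. The eligibility changes listed for Amendment 1 touch neither 4.1.5 nor 4.2.4, so both are current.
2. *Does another section set the start of ART?* No. Section 5.4.4 asks clinicians to work towards ART during treatment, but names no day and no check before dosing.
3. *Does another section require the test?* No. The screening advice in 6.1.6 is drug information. No study procedure turns it into a test for HIV-infected patients.

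The number of patients in the left-hand column is the trial's HIV-infected patients multiplied by the share of them not on ART at day 1. The second factor is not in the documents. Section 1.2 gives 67% of HIV-infected people in Malawi on ART, but that is a national figure, not one for patients with multicentric Castleman disease (MCD). The same section links MCD to longer time on ART than Kaposi sarcoma or lymphoma, which points to a small share without fixing it.

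**The case against.** The strongest reply is that a site must apply every criterion (section 4.0). Item 4.2.4 says HIV-infected patients must already be taking one of the two drugs, and the opening of 4.2 ties the exclusions to enrollment. A careful site would then not dose an uncovered patient. This reading is available, so it cannot be said that the plan *will* treat such patients uncovered. It does not settle the matter, because 4.2.4 presents the requirement as a restatement of the inclusion criteria, and those are looser.

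A reader might infer instead that the strict reading simply turns these patients away, since 11.4.2 allows no eligibility exceptions. That also goes too far. Screening may run for up to 21 days before enrollment, and a patient who starts ART in that time satisfies both criteria.

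Section 5.4.4 is a real mitigation: a patient enrolled before starting should be on ART during treatment. The advice in 6.1.6 may also prompt a clinician to test. What is missing is a scheduled HBsAg test, which does not mean that no result could exist.

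Two stronger claims about size are tempting, and the documents do not support either.

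- *A count of 22 to 27 patients.* This is 27 × 0.83 = 22.4 (the HIV-infected share in the French cohort cited in 1.2) up to 27 × 1.00 = 27 (the group's own cohort, 25 of 25). It counts everyone without a scheduled HBsAg test, including those already covered by ART, for whom the protocol deliberately substitutes cover for testing.
- *Hepatitis falling after the last liver test but inside the 12-week safety window.* Section 6.1.6 gives two medians. About one month after the last dose is day 22 + 30 = day 52. About four months after initiation is 4 × 30 = day 120, beyond 12 × 7 = day 84. The last scheduled bilirubin is at end of treatment: "End-of-treatment visit should occur 7-14 days from final dose of chemotherapy", that is day 29 to 36, or as late as day 43 with the 7-day visit allowance. The gap to day 52 is therefore 52 − 29 = 23 days down to 52 − 43 = 9 days, and it rests on one of the two medians. A patient who starts ART during the four treatment weeks would also be on an active drug well before day 52. The scenario needs a carrier who stays off ART, contrary to 4.1.5 and 5.4.4.

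**Conclusion.** The conflict is real and stands in the current text. The HIV-negative-only testing in 7.2.4 and Table 7 rests on a safeguard that 4.2.4 attributes to the inclusion criteria and that 4.1.5 does not supply. On the looser reading, an HIV-infected patient not yet on ART may receive the first rituximab dose with no scheduled HBsAg test and no drug active against hepatitis B. On the stricter reading, that patient must start ART before enrollment or be excluded. The documents do not choose between them.

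The number affected is unknown and probably small. It depends on ART coverage at day 1 among MCD patients, and any harm also depends on HBsAg prevalence; neither is given, so no number of carriers or reactivations is claimed. The primary endpoint, power and sample size are unchanged. The point deserves correction because the possible harm is grave and the remedy is cheap. It does not show that the trial is unsafe as designed.

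**What to change.** Give 4.1.5 and 4.2.4 the same rule: an HIV-infected patient must have started ART containing tenofovir or lamivudine, with the start documented, on or before day 1 and before the first rituximab dose. Add a cross-reference in 5.4.4. HIV clinicians would still prescribe; the protocol would only make the start a condition of dosing.

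The documentation adds little work, because section 7.1.1 already records medication dates. The real cost is a possible short delay to rituximab in a symptomatic flare if the HIV clinic cannot start ART by day 1.

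Where that delay is clinically unacceptable, allow an alternative: a baseline HBsAg test limited to HIV-infected patients not yet on ART, with the 4.2.4 exclusion applied to them. A patient who tests negative could proceed; one who tests positive would first need tenofovir or lamivudine. The assay is already in the protocol, so this needs only a matching line in 7.2.4 and Table 7. Neither option changes the sample size or the analysis.

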5.0 TREATMENT PLAN

5.1 Schema

[figure not shown]

Figure 4. Clinical trial schema for newly diagnosed patients with MCD requiring treatment.
"High-risk disease" defined as ECOG performance status >2 or hemoglobin <8 g/dL.

Clinical trial schema for newly diagnosed patients with MCD requiring treatment.

¹ "High-risk disease" defined as ECOG performance status >2 or hemoglobin <8 g/dL at the time of screening or enrollment labs. Note that a patient receiving a blood transfusion due to hemoglobin <8 g/dL within 1 month of enrollment will be considered high-risk.

² See Time and Events Table (8.1) for detailed study visit components.

³ MCD-SS=MCD symptom score

We will conduct a single arm, phase II clinical trial for safety and efficacy of risk-stratified treatment with rituximab +/- chemotherapy for MCD. Eligible patients will be enrolled and treated according to the study schema. High-risk patients (defined as patients with ECOG performance status >2 or hemoglobin <8 g/dL at the time of screening or enrollment labs)^{9,10,13-16} will receive four weekly doses of rituximab (375 mg/m²) and etoposide (100 mg/m²) as in Bower, et al.⁹ Low-risk patients will receive the same dose of rituximab alone.

The planned sample size is 27 patients and the primary outcome is safety. Secondary outcomes include one- and two-year EFS (combination of relapse, development of NHL, or death), OS, and KS exacerbation rates.

We will also collect clinical, laboratory, virologic data, and stored samples at baseline and end-of-treatment to both describe the presentation of MCD in our population and to evaluate risk factors for death or relapse.

Finally, we will conduct comprehensive microcosting analysis and a Markov model cost-effectiveness analysis.

5.2 Treatment Dosage and Administration

Treatment will be administered on an outpatient basis in the Kamuzu Central Hospital cancer clinic, as per **Table 1**, where chemotherapy is currently administered.

Table 1: REGIMENT DESCRIPTION			
Agent	Premedications	Dose and Route	Schedule
Rituximab	Premedicate with diphenhydramine 50 mg IV and acetaminophen 650 mg PO 1 hour prior to rituximab.	
375 mg/m² rounded to the nearest 100 mg to avoid vial waste (dilute in normal saline or 5% dextrose to a final concentration of 1-4 mg/ml).
 
Administer via slow IV infusion, starting at 50mg/hr and increasing by 50mg/hr every 30 minutes to a maximum infusion rate of 400mg/hr.
 
CAUTION: DO NOT ADMINISTER AS AN INTRAVENOUS PUSH OR BOLUS. IV pumps such as the IMED 960 may be used with the rituximab infusion.
 
DO NOT INFUSE CONCOMITANTLY with another IV solution or IV medications. Prime the line with the rituximab solution such that approximately 30 mL are delivered. This will saturate the filter and tubing.
	Days 1, 8, 15, 22
Etoposide	n/a	
100 mg/m² (dilute to final concentration 0.2-0.4 mg/mL in either normal saline or 5% dextrose)
 
IV over 1 hour after completion of rituximab
	Days 1, 8, 15, 22

5.3 Toxities and Dosing Delays/Dose Modifications

Any patient who receives treatment on this protocol will be evaluable for toxicity. Each patient will be assessed periodically for the development of any toxicity according to the Time and Events table (Section 8.1). Toxicity will be assessed according to the National Cancer Institute (NCI) CTCAE, v5.0. Dose adjustments should be made according to the system showing the greatest degree of toxicity. See **Tables 2-4** below for recommended dose delays/dose modifications.

Assigning cause of death is often difficult in Malawi because diagnostic capabilities are limited and deaths frequently occur outside of health facilities. To address this challenge, two senior non-study clinicians will be enlisted to review all study data for deceased patients and assign cause of death as either likely treatment-related, MCD-related, related to another cause, or unable to determine. In the event of discordant conclusions, a third senior clinician will serve as a tiebreaker.

Table 2: Hematological toxicity dose reductions		
ANC	Platelets	Action
≥ 0.5 x 10 ³ /µL	≥ 50 x 10 ³ /µL	None.

$< 0.5 \times 10^3/\mu\text{L}$	$< 50 \times 10^3/\mu\text{L}$	
FIRST EPISODE: Hold current etoposide dose until ANC $\geq 0.5 \times 10^3/\mu\text{L}$ and platelets $\geq 50 \times 10^3/\mu\text{L}$. Restart next treatment at 75 mg/m^2. Do NOT hold or reduce rituximab dose.
 
SECOND EPISODE: Hold current etoposide dose until ANC $\geq 0.5 \times 10^3/\mu\text{L}$ and platelets $\geq 50 \times 10^3/\mu\text{L}$. Restart next treatment at 50 mg/m^2. Do NOT hold or reduce rituximab dose.
 
Goal is to replace doses and complete full course of four doses of both etoposide and rituximab.

---------------------------------	--------------------------------	--

Table 3: Non-hematological toxicity dose reductions for rituximab	
NCI CTC Grade	
0-2	No change from original dose.
3-4	Wait until resolved to \leq Grade 2, no dose reduction.
Second episode of Grade 3 or 4 toxicity	Hold until resolved to \leq Grade 2, no dose reduction.
Third episode of Grade 3 or 4 toxicity	Remove subject from trial

Table 4: Hepatic and renal dysfunction dose adjustment for etoposide	
Event	Action
Renal dysfunction	
Cr clearance $>50 \text{ ml/min}$	None
Cr clearance 15-50 ml/min	Decrease dose to 75 mg/m^2
Cr clearance $<15 \text{ ml/min}$	Decrease dose to 50 mg/m^2
Hepatic dysfunction	
Bilirubin $<1.5 \text{ mg/dL}$	None
Bilirubin 1.5-3.0 mg/dL	Decrease dose to 50 mg/m^2
Bilirubin $>3.0 \text{ mg/dL}$	Hold until bilirubin $<3.0 \text{ mg/dL}$

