3.0 STUDY ENDPOINTS

3.1 Primary Endpoint

Safety will be classified and graded by non-hematologic Grade ≥ 3 AEs (CTCAE v5.0) and treatment-related mortality through twelve weeks from the start of rituximab with or without etoposide therapy.

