10.3 Safety monitoring

Sequential boundaries will be used to monitor the rate of treatment-related mortality and non-hematologic AEs. Accrual to the study will be suspended until the study PI, co-investigators and the DSMC can review the data, and determine if the study should continue, be amended, or be closed to further accrual if excessive numbers of these events are seen (i.e., the number of deaths or the number of non-hematologic AEs is equal to or exceeds b_n out of n patients with full follow-up (**Table 8**)). The boundaries for treatment-related mortality rate are Pocock-type stopping boundaries that yield the probability of crossing the boundary at most 0.05 when the death rate is equal to the acceptable rate (0.10). The boundaries for the rate non-hematologic AEs are Pocock-type stopping boundaries that yield the probability of crossing the boundary at most 0.05 when the death rate is equal to the acceptable rate (0.40). The bounds are non-binding, and provide a guideline that may result in study modification or closure.

Table 8: Pocock-stopping bounds for deaths and adverse events.

Number of Patients, n	1	2	3	4	5	6	7	8	9	10	11	12	13	14	15	16	17	18	19	20	21	22	23	24
Boundary Treatment-related mortality, b_n	-	2	2	2	2	3	3	3	3	3	3	4	4	4	4	4	4	4	4	5	5	5	5	
Boundary Grade ≥ 3 non-hematologic adverse events b_n	-	-	-	-	5	6	6	7	8	8	9	9	10	10	11	11	12	13	13	14	14	15	15	

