10.4 Data Analysis Plans

10.4.1 Primary Objective: To describe the safety, as determined by the rate of Grade ≥ 3 non-hematologic AEs and treatment-related mortality, of a risk-adjusted approach to the treatment of MCD with rituximab (375 mg/m² weekly for four weeks) +/- etoposide (100 mg/m² weekly for four weeks) in Malawi.

The rate will be estimated for individual AEs and a summation of Grade ≥ 3 non-hematologic AEs will be estimated along with a 95% confidence interval.

The rate of treatment-related mortality will be estimated along with a 95% confidence interval around the point estimate.

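### The plan does not say how deaths of undetermined cause enter treatment-related mortality, and Section 10.3 names two different counts for the mortality boundary

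*Combined protocol and SAP*

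**What the plan says.** Section 3.1 makes "treatment-related mortality through twelve weeks from the start of rituximab", with or without etoposide, part of the primary endpoint. Section 10.4.1 gives its analysis: "The rate of treatment-related mortality will be estimated along with a 95% confidence interval around the point estimate". TRM has no hypothesis test and no power statement.

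Section 5.3 explains why attribution needs a procedure: "Assigning cause of death is often difficult in Malawi because diagnostic capabilities are limited and deaths frequently occur outside of health facilities". Two senior clinicians from outside the study review the data and "assign cause of death as either likely treatment-related, MCD-related, related to another cause, or unable to determine". If they disagree, "In the event of discordant conclusions, a third senior clinician will serve as a tiebreaker". The undetermined category is therefore an allowed final result, separate from the treatment-related one. Nothing in Sections 3.1, 5.3, 10.3 or 10.4.1 links the four categories to the TRM numerator, and no sensitivity analysis is planned.

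Section 10.3 opens with "Sequential boundaries will be used to monitor the rate of treatment-related mortality and non-hematologic AEs", and the Table 8 row is labelled treatment-related mortality. The condition that suspends accrual, however, is that "the number of deaths or the number of non-hematologic AEs is equal to or exceeds" the boundary value b_n. The calibration sentence describes bounds for the TRM rate but states the acceptable value of 0.10 as a death rate. The bounds are described as non-binding.

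**The concern.** There are two gaps, and they compound each other.

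First, a component of the primary endpoint depends on a four-way classification, and one of the four results has no assigned place in the calculation. The plain reading is that TRM means deaths rated likely treatment-related. Under that reading an undetermined death stays in the denominator and leaves the numerator, so it is treated as not treatment-related. With about 24 evaluable patients, one or two deaths move the estimate materially. If the rule is left open, it may be chosen after the deaths are known.

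Second, the monitoring committee cannot tell from Section 10.3 which count to compare with b_n. A count of all deaths and a count of treatment-related deaths differ by the undetermined deaths, and also by those attributed to the disease or to another cause. The decision to pause accrual could turn on which phrase is followed.

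**Working it through.** **Inputs from the documents.** The Table 8 mortality row has no bound at n = 1, then 2 for n = 2-5, 3 for n = 6-11, 4 for n = 12-19 and 5 for n = 20-23. The available text shows 23 entries under 24 column numbers; I read them as n = 1-23 and checked other placements below. The stated calibration is a crossing probability of at most 0.05 at a rate of 0.10. The evaluable sample is 24 (Section 10.2).

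**Assumptions, not in the documents.** The true TRM is p, and u is the share of truly treatment-related deaths that reviewers rate as undetermined. Patients are independent, and the bound is checked after each patient.

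**Method.** If only likely treatment-related deaths count, the counted rate is q = p(1 - u). Let f_n(c) be the probability of c counted deaths among n patients with no earlier crossing. Then f_n(c) = (1 - q) f_{n-1}(c) + q f_{n-1}(c - 1). At each n, the mass with c >= b_n is moved to the crossing probability.

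**The plan's own figure.** At q = 0.10 the printed row is crossed with probability 0.185, against the stated maximum of 0.05. Over all monotone placements of the missing entry the range is 0.185-0.220. The stated calibration is not reproduced. That is a separate issue; here the row is used as printed.

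**If undetermined deaths are not counted**, the probability of triggering review is:

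| True TRM p | u = 0 | u = 10% | u = 25% | u = 50% |
|---|---|---|---|---|
| 0.10 | 0.19 | 0.15 | 0.10 | 0.04 |
| 0.20 | 0.64 | 0.56 | 0.41 | 0.19 |
| 0.25 | 0.81 | 0.74 | 0.59 | 0.29 |

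For example, p = 0.20 and u = 25% give q = 0.20 × 0.75 = 0.15 and a crossing probability of 0.41. Placing the missing entry elsewhere leaves the pattern intact: at p = 0.20 the values are 0.64-0.69 for u = 0, 0.41-0.46 for u = 25% and 0.19-0.22 for u = 50%.

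**If all undetermined deaths are counted and some are unrelated.** Take p = 0.10 plus an assumed 5% of patients with an unrelated, undetermined death. The counted rate is 0.10 + 0.05 = 0.15, and crossing rises from 0.19 to 0.41.

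**Primary estimate, illustrative counts at n = 24 with exact 95% intervals** (the plan does not name an interval method):
- 2 likely treatment-related deaths: 2/24 = 8.3% (1.0-27.0%).
- With 1 undetermined death added: 3/24 = 12.5% (2.7-32.4%).
- With 2 added: 4/24 = 16.7% (4.7-37.4%).

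A single coding decision can thus move the point estimate across the 10% rate that Section 10.3 calls acceptable, although the intervals overlap widely.

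**Not affected.** The sample size concerns only the adverse-event component. With n = 24 and rejection at 6 or fewer events, the exact alpha is 0.096 and the power 0.811, in line with Section 10.2.

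**The case against.** A reader might go further and infer that the plan removes undetermined deaths from TRM, that the boundary is therefore blunted, and that the protocol expects such deaths to be common. The documents support none of these as stated.

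- Exclusion is an inference from silence. It is the plain reading of the categories, but it is not a written rule.
- Loss of boundary sensitivity holds under only one of two conflicting readings. Taken literally, the trigger counts deaths, so undetermined deaths count and nothing is lost. The primary TRM rate would still depend on attribution.
- Section 5.3 says cause is often hard to assign and sets up the review panel for that reason. It gives no expected undetermined share.
- The error need not run one way. Undetermined deaths may be due to the disease or to infection, and counting them all can overstate TRM, as the 0.19 to 0.41 example shows.
- At 10% true TRM, losing half of the deaths brings the printed row to 0.04, inside its stated limit. That is the accidental offset of a separate calibration error, not a safeguard. A row loosened to meet its stated limit would make undercounting matter more.
- Counting loss to follow-up as failure for EFS and OS (Section 10.5.2) is a weak parallel. It concerns whether a death occurred, not its cause.

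There are other safeguards. Every death is a serious adverse event with notification within 24 hours, the DSMB reviews safety data, and overall survival is assessed at 12 weeks. Section 3.1 does not limit Grade 3 or higher events to related ones, so an undetermined death might also count there, although Section 1.1 says treatment-related. These reduce the risk that a harmful pattern goes unseen. They do not define the TRM numerator or settle which count is compared with b_n.

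**Conclusion.** The point holds as two omissions of definition: undetermined deaths have no stated place in a primary safety rate, and Section 10.3 gives two counts for one boundary. The contradiction and the silence are plain on the page and need no assumption.

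The size is conditional. It requires that only likely treatment-related deaths count and that some undetermined deaths are truly treatment-related. Then, at an assumed 20% true TRM, the chance of triggering review falls from 0.64 to 0.41 (25% undetermined) or 0.19 (50%). Under the same counting rule the estimated rate can only stay the same or fall. Whether it is then too low depends on the true causes, which the trial may not be able to establish. Neither extreme should therefore stand as the only estimate.

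This should be settled before the data are analysed. Sample size and power do not change.

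**What to change.** 1. In Section 10.3 and Table 8, use one term for the count compared with b_n. For this non-binding review trigger, define it as deaths within 12 weeks of starting treatment that are rated likely treatment-related or undetermined.
2. In Section 10.4.1, report the 12-week TRM with its 95% confidence interval twice: without undetermined deaths as the lower bound, and with them as the upper bound. State that neither is the sole estimate.

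The text change is a few sentences, with no new data and no change to the sample size. The cost is more pauses for review when undetermined deaths are in truth unrelated: crossing rises from 0.19 to 0.41 at 10% true TRM plus an assumed 5% of such deaths. The reported TRM range will also be wider. The calibration of the printed mortality row needs its own correction and is not resolved by this change.
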